9.4 Imputation of Missing Data

In this Phase I PK study, missing observations will be assumed to be missing completely at random (MCAR). No action will be taken to handle missing data. A participant who withdraws prior to the

last planned observation in a study period will be included in the analyses up to the time of discontinuation.

10 Study Participants

The subsections in this section include specifications for reporting participant disposition and study intervention/study discontinuations. Additionally, procedures for reporting protocol deviations are provided.

10.1 Disposition of Participants and Discontinuations

The following will be presented in a summary table:

- Total number of participants screened (i.e., participants who gave informed consent)
- Number of screened participants who discontinued from the study prior to first dosing overall and grouped by the main reason for discontinuation:
 - Participant did not meet all eligibility criteria
 - Withdrew consent
 - Other (COVID-19-related and COVID-19-non-related)
- Number of treated participants
- Number and percentage of treated participants who completed study
- Number and percentage of treated participants who discontinued the study or study intervention, with the primary reason of discontinuation:
 - Adverse event
 - Lost to follow-up
 - Protocol non-compliance
 - Death
 - Withdrew consent
 - Other (COVID-19-related and COVID-19-non-related)

A listing of discontinued participants will be provided.

A listing of participants affected by COVID-19-will also be provided. The start of COVID-19 pandemic will be defined by 11th of March 2020 when the WHO declared COVID-19 as pandemic.

The number and percentage of participants will be presented by group of study intervention and total, where applicable. Percentages will be presented with respect to the number of treated participants, where applicable.

10.2 Protocol Deviations / Exclusion from Analysis Sets

10.2.1 Important Protocol Deviations

Listings of important protocol deviations will be provided including the date and relative day in relation to dosing in the relevant period. A distinction will be made between important protocol deviations due to COVID-19 versus not due to COVID-19. The respective important protocol deviations will be flagged accordingly.

Important protocol deviations or important events that might influence PK include, but may not be limited to the following:

- Adverse events, diarrhea etc. (these instances will be discussed on a case-by case basis)
- Vomiting after administration following oral dosing (these instances will be discussed in alignment with applicable regulatory guidelines on a case-by-case basis)
- Sample processing errors that may lead to inaccurate bioanalytical results
- Inaccurate dosing or dosing errors (e.g., dose administration delayed, dose change or missed doses)
- Predose or trough sample collected after the actual dosing
- Non-compliance with food and drink requirements (e.g., non-fasted, incomplete meal consumption, caffeine intake)
- Concomitant medication, vitamins, dietary or herbal supplements

Should one or more of these events be available at the Data Review Meeting, its implication for PK evaluation will be discussed and agreed amongst relevant study team members (e.g., Sponsor Clinical Pharmacology/Biostatistics/Clinical Pharmacokinetics & Pharmacodynamics team representative). Appropriate action will be taken such as flagging individual values to be excluded from analysis.

10.2.2 Reasons Leading to the Exclusion from an Analysis Set

All criteria/reasons leading to the exclusion of a participant from an analysis set will be listed based on the Safety Analysis Set.

If participants are excluded from the PK Analysis Set, the reasons for exclusion will be listed.

Reasons for excluding individual PK concentrations will also be listed separately and flagged in the main listing.

11 Demographics and Other Baseline Characteristics

Demographics and baseline characteristics will be presented for the SAF.

11.1 Demographics

Descriptive statistics will be presented for age, height, weight, and BMI. Frequency counts and percentages will be presented for sex, race, and ethnicity. The summary will be performed overall.

BMI (kg/m²) will be derived (i.e., not taken directly from the database) according to the following formula:

$$\text{BMI [kg/m}^2\text{]} = \frac{\text{weight [kg]}}{\text{height[cm}^2\text{]}} \times 10000$$

11.2 Medical History

Medical history will be coded using the Medical Dictionary for Regulatory Activities (MedDRA), most current version at time of data base lock, and listed. The medical history will be listed by participant including preferred term (PT) as event category and system organ class (SOC) body term as Body System category.

11.3 Other Baseline Characteristics

Other baseline measurements, such as virus screen, cotinine, alcohol and drugs of abuse screen, eGFR, and pregnancy test in women will be listed.

12 Previous or Concomitant Therapies/Procedures

Medications will be presented for the Safety Analysis Set.

Previous medications are defined as any medication discontinued prior to the administration of study intervention. Concomitant medications are defined as any medication taken during the course of the study, with a starting date greater than or equal to the administration of study intervention, or with a starting date prior to the administration of study intervention and ongoing at the time of the administration of study intervention.

The World Health Organization Drug dictionary (WHO-DD) most current version at time of database lock, will be used for coding of prior and concomitant medications and they will be described using PT as applicable.

Previous and concomitant medications will be listed. Concomitant procedures, if any, will also be listed. The following information will be displayed in a listing: generic or trade name (as reported in CRF), WHO drug name (including ATC coding and PT), dose/unit, route, frequency, reason for use, start/end date and time

13 Study Intervention: Compliance and Exposure

The dosing of each participant is monitored by the study nurse or investigator. A listing of date and time of each drug administration and each blood sampling, including time deviations as well

as measured plasma concentrations, will be provided sorted by participant. Information on meal intake will be listed by participant, if provided.

14 Efficacy Analyses

Not applicable.

15 Safety Analyses

This section includes specifications for summarizing safety endpoints that are common across clinical studies such as adverse events, laboratory tests, and vital signs.

All safety analyses will be performed for the Safety Analysis Set.

Safety analyses will be done according to the as-treated principle.

15.1 Adverse Events

All AEs recorded during the study will be coded with the MedDRA, latest version at time of database lock, and assigned to a SOC and a PT.

TEAEs are those events with onset dates on or after the first administration of study intervention on Day 1. Any AE occurring before the administration of study intervention on Day 1 and resolved before administration of study intervention or not worsening after administration of study intervention on Day 1 will be included in the AE listings but will not be included in the summary tables (unless otherwise stated). These will be referred to as “pre-treatment” AEs.

In case AE-related dates are partial, the available information will be used in a conservative approach to determine whether the AE is treatment-emergent.

All analyses described in Section 15.1 will be based on TEAEs if not otherwise specified. The AE listings will include all AEs (whether treatment-emergent or not). AEs outside the on-treatment period will be flagged in the listings.

Unless otherwise specified, TEAEs will be summarized by number and percentage of participants with the TEAE in the category of interest, as well as the number of events, in total by primary SOC and PT in alphabetical order for SOC and decreasing overall frequency for PT.

If an event was reported more than once due to change in intensity and change in relationship, the worst severity and the worst relationship to study intervention will be tabulated.

Each participant will be counted only once within each SOC or PT.

15.1.1 All Adverse Events

The number and percentage of participants experiencing at least one TEAE as well as the number of events will be summarized by study intervention and overall:

- The number and percentage of participants with any TEAE, any related TEAE, any serious TEAE, any related serious TEAE, any severe TEAE, any related severe TEAE, any AESI, any TEAE leading to death, any related TEAE leading to death, any TEAE leading to study discontinuation.
- The number and percentage of participants with at least one TEAE and the number of events by SOC and PT.
- The number and percentage of participants with TEAEs excluding SAEs and the number of events, with frequency $\geq 5\%$ in any study intervention arm by SOC and PT
- The number and percentage of participants with at least one TEAE and the number of events by severity, SOC, and PT
- The number and percentage of participants with at least one related TEAE and the number of events by SOC and PT
- The number and percentage of participants with at least one AESI recorded and the number of events by SOC and PT.

Unless otherwise stated, AEs will be displayed with SOC terms sorted alphabetically and PTs within each SOC term sorted in descending overall frequency.

For determining incidence counts, within each level of TEAE term, if a participant experiences more than one occurrence, the participant will only be counted once for that TEAE.

AEs related to any study intervention are those events with relationship missing, unknown or yes.

In case a participant had events with missing and non-missing severity, the maximum non-missing severity will be displayed.

15.1.2 Adverse Events Leading to Discontinuation of Study Intervention

TEAEs leading to permanent discontinuation of study treatment will be summarized by treatment and overall including number of participants, percentage, and number of events.

A listing of TEAEs leading to permanent discontinuation of a study treatment will additionally be provided.

15.2 Deaths, Other Serious Adverse Events, and Other Significant Adverse Events

15.2.1 Deaths

A listing of deaths, if any, will be provided.

15.2.2 Serious Adverse Events

A summary table of serious adverse events (SAEs), if any, by treatment and overall will be provided displaying the number and percentage of participants by treatment with at least one SAE and the number of SAEs overall and by SOC and PT. SOC terms and PTs within each SOC term will be sorted alphabetically.

Listing of SAEs, if any, will be provided.

15.2.3 Other Significant Adverse Events

The following AESI were defined:

- Infections (serious, severe, and opportunistic, \geq Grade 3)
- Seizures
- Elevated lipase, elevated amylase, pancreatitis
- Liver-related events

More information can be found in the CSP, Section 8.3.7.

AESIs will be flagged based on an external excel file which includes the precise descriptions of the AESIs (SMQs, PTs and laboratory constellations) and will be used to retrospectively identify AESIs in the AE listings. Summary table of the number and percentage of participants with at least one AESI by SOC and PT will also be provided.

15.3 Clinical Laboratory Evaluation

Listings and summary statistics at each assessment time will be presented using SI units. Normal ranges will be provided by the laboratory department, and out of range flags will be calculated based on the normal ranges. Laboratory data not transferred from the central laboratory in SI units will be converted to SI units before processing. Both original units and SI units will be provided in the SDTM domain.

Laboratory parameters will be listed by participant and time-point and flags for measurements outside the reference ranges, where applicable, and summarized indicating the study intervention at the respective time-point using descriptive statistics for absolute values.

Safety laboratory parameters are separated into:

- Hematology (including coagulation)
- Biochemistry

- Urinalysis
- Other tests

Tables will be produced for Hematology and Biochemistry laboratory parameters. Listings of abnormal test results (low and high) will also be provided.

15.4 Vital Signs

Vital signs data will be summarized by treatment and time point using descriptive statistics for baseline (see definition in Section 9), each evaluation during the study, and change from baseline to each evaluation. Listings of vital sign data will be provided.

Vital sign summaries will include all vital sign assessments from the on-treatment period. All vital sign assessments will be listed, and those collected outside the on-treatment period will be flagged in the listing.

Tympanic temperature will be listed by participant and time-point.

15.5 Other Safety or Tolerability Evaluations

Safety ECG data will be summarized by study intervention and time point using descriptive statistics for baseline (see definition in Section 9), each evaluation during the study, and change from baseline to each evaluation. Listing of safety ECG data will be provided.

ECG summaries will include all ECG assessments from the on-treatment period. All ECG assessments will be listed.

The analysis of QT data is complicated by the fact that the QT interval is highly correlated with heart rate. Because of this correlation, formulas are routinely used to obtain a corrected value, denoted QTc, which is independent of heart rate. This QTc interval is intended to represent the QT interval at a standardized heart rate. Several correction formulas have been proposed in the literature. The QT interval will be corrected for heart rate by the Fridericia's formula, QTcF, is defined as

$$QTcF = \frac{QT}{\sqrt[3]{RR}},$$

where RR represents the RR interval of the ECG, in seconds, and can be estimated as 60/Heart Rate.

Investigator reported interpretation results will also be tabulated by study intervention and time point using the number and percentage of participants for each interpretation category (Normal, Abnormal Not Clinically Significant [NCS], Abnormal Clinically Significant [CS]). Abnormality reason will also be displayed.

16 Analyses of Other Endpoints/Estimands

16.1 Pharmacokinetics

PK evaluation will be performed by Nuvisan GmbH.

All statistical analyses and descriptive summaries of PK data will be performed on the PK Analysis Set.

16.1.1 Descriptive Statistics of PK Concentration Data

Concentrations of evobrutinib will be descriptively summarized by study intervention using number of observations (n), arithmetic Mean, SD, CV%, Min, Median, Max, geometric mean (GeoMean), the geometric coefficient of variation (GeoCV%) and the 95% confidence interval (CI) for the GeoMean (LCI 95% GM, UCI 95% GM). Descriptive statistics will only be calculated for $n > 2$ in which a measurement of BLQ represents a valid measurement and will be taken as zero for summary statistics of PK concentration data.

Any mean or median value that is below the lower limit of quantification will be shown as BLQ.

Descriptive statistics of PK concentration data will be calculated using values with the same precision as the source data and rounded for reporting purposes only. In export datasets, as well as in the SDTM PC domain, PK concentrations will be provided with full precision and will not be rounded.

The following conventions will be applied when reporting descriptive statistics of PK concentration data:

n	0 decimal place
Mean, Min, Median, Max:	3 significant digits
SD:	4 significant digits
CV%:	1 decimal place

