## Evobrutinib (M2951) Relative Bioavailability of Evobrutinib Tablet Batches

MS200527\_0131

Assessment	Screening	Treatment								SFU by phone	Comments	
		P1		P2		P3		P4				
Study Day(s)	-28 to -2	-1	1	2	3	4	5	6	7	8	15 ± 3	Approximate 48-hour washout between doses on Days 1, 3, 5, and 7.
Period-specific Day(s)	-28 to -2	-1	1	2	1	2	1	2	1	2		
Administration of study intervention			X		X		X		X			Washout period of 48 hours.
Physical examination	X	X							X			A full physical examination will be performed at Screening and before discharge on Day 8, and a brief physical examination will be performed on Day -1.
Vital signs	X	X	X		X		X		X	X		Vital signs will be assessed on the days of dosing (Day 1, 3, 5, and 7) at predose and at 2 hours postdose. At visits where assessment time points coincide with each other, the following sequence of activities will be followed: 12-lead ECG followed by vital signs within 30 minutes before the specified time point preceding the PK sampling, which will be performed at the specified time point.
Safety ECG	X	X	X		X		X		X	X		12-lead ECG will be performed on the days of dosing (Day 1, 3, 5, and 7) at predose and at 2 hours postdose. See Vital signs (row above) for assessments that coincide.
Clinical laboratory safety tests	X	X					X		X			On Day 5, tests will be performed predose. Blood samples for the clinical laboratory safety assessments will be collected in a fasted condition.
PK sampling			X	X	X	X	X	X	X	X		Plasma samples for PK analysis will be collected on the days of dosing (i.e., Days 1, 3, 5, and 7) at predose and 0.25, 0.5, 1.0, 1.5, 2.0, 2.5, 3.0, 4.0, 6.0, 8.0, 12.0, 16.0, and 24.0 hours postdose. See Vital signs (row above) for assessments that coincide.
Previous medication	X											
Concomitant medication monitoring	X	<=====>						X				
AE monitoring	X	<=====>						X				

AE=Adverse Event, Day = Study Day, ECG = Electrocardiogram, eGFR = estimated Glomerular Filtration Rate;FSH = Follicle stimulating hormone, P=Period, PK=Pharmacokinetics.

CONFIDENTIAL  
INFORMATION

10/60

Global Version ID: CCI

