
**Evobrutinib (M2951)    Relative Bioavailability of Evobrutinib Tablet Batches**  
**MS200527\_0131**

Category	Criterion
	
13. Administration of live vaccines or live-attenuated virus vaccines within 3 months prior to Day 1. Administration of other types of vaccines is allowed until 14 days before the first administration of study intervention, thereafter it is prohibited until the end of the study. However, for SARS-CoV-2 mRNA vaccine is not permitted 42 days prior to Day1.
 
Note: In case of clinical symptoms, the participant should be symptom-free for at least 1 week prior to the first administration of study intervention.

Prior/Concomitant Therapy	
14. Moderate or strong inhibitors or inducers of CYP3A4/5 or Pgp within 4 weeks prior to the first administration of study intervention.
 
15. Use of any prescribed medicine or over-the-counter drug or dietary supplement, including herbal remedies, vitamins, and minerals, antacids and dietary supplements such as fish oils within 2 weeks or 5 times the half-life of the respective drug, whichever is longer, prior to the first administration of study intervention.
 
Occasional paracetamol (acetaminophen) up to 2 g per day or hormonal contraceptives/HRT is permitted.

Prior/Concurrent Clinical Study Experience	
16. Use of any investigational drug in any clinical study within 60 days prior to Day 1 administration, or have used an experimental monoclonal antibody within the past 1 year prior to Day 1, or have participated in a study evaluating a BTK inhibitor within 60 days, or are on extended follow-up in a clinical study, even if last administration of a study intervention was more than 60 days ago, or 5 half-lives of the investigational drug, whichever is longer, prior to the first administration of study intervention.

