### 6.3 Measures to Minimize Bias: Study Intervention Assignment and Blinding

#### 6.3.1 Study Intervention Assignment

This will be an open-label, randomized study. Participants will be randomly assigned to 1 of the following 4 treatment sequences, with a maximum of 7 participants assigned to each treatment sequence (ratio 1:1:1:1), using a Williams design for a 4-treatment, 4-period crossover study:

Sequence no.	Actual Sequence	Period			
		1	2	3	4
1	A-B-C-D	A	B	C	D
2	B-D-A-C	B	D	A	C
3	C-A-D-B	C	A	D	B
4	D-C-B-A	D	C	B	A

Batch A = **CCI** (reference), Batch B = **CCI** (lower dissolution bound), Batch C = **CCI** (upper dissolution bound), Batch D = **CCI** (hammer-milled).

After informed consent procedure, every participant is given a screening number. Only participants who comply with all eligibility criteria (see Sections 5.1 and Section 5.2) can be included into the study.

On Day 1, prior to first administration, the participants enrolled will be assigned a unique 3-digits assignment number (randomization number) in ascending numerical order at the study site. The

randomization number encodes the participant's assignment to 1 of the 4 treatment sequences of the study, per the randomization schedule generated prior to the study by PPD [REDACTED] CTS Department.

The Investigator will keep a record relating the participant assignment numbers and the names of all participants (including screening number and the PPD [REDACTED] randomization number) who have given their informed consent, to allow easy checking of data in participant files, when required. This record will also include the date of participant's enrollment and completion, as well as participants who could not be assigned to study intervention for whatever reason.

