16.1.4 General Specifications for PK Concentration and PK Parameter Data

Predose samples that occur before the first drug administration will be assigned a time of 0 hours, as if the sample had been taken simultaneously with the study intervention administration.

Predose or trough samples which have been taken after the subsequent dosing will be reported as a protocol deviation. The resulting concentrations will be included in concentration listings but excluded from descriptive statistics of concentrations and from PK parameter estimation.

Values BLQ will be taken as zero for summary statistics of PK concentration data, PK parameter estimation (e.g., AUC) and for graphical presentations.

Missing concentrations (e.g., no sample, insufficient sample volume for analysis, no result or result not valid) will be reported generally as "N.R.". A participant who withdraws prior to the last planned observation will be included in the analyses up to the time of discontinuation if still included in the PK analysis set.

If samples are collected outside of the PK sampling time windows defined in the CSP in Section 8.4, these will be included in the PK parameter estimation (NCA) but will be excluded from the concentration summary and mean/median concentration plots.

PK concentrations which are erroneous due to a sampling processing or analytical error (as documented in the bioanalytical report) may be excluded from the PK analysis if agreed by the Sponsor. In this case the rationale for exclusion will be provided in the CSR. Any other PK concentrations that appear implausible to the Clinical Pharmacologist/Clinical PK/PD Scientist will not be excluded from the analysis. Any implausible data will be documented in the CSR.

If important protocol deviations occurred likely to affect the PK profile of participants as specified in Section 10.2.1, the impacted concentrations and PK parameters will be excluded from summary statistics and further statistical evaluation.

Any PK concentrations or PK parameters excluded from summary statistics will be included in participants listings and flagged; a reason for exclusion will be detailed in the CSR (e.g., a footnote or a table of exclusions). Any flags will be included in the study specific CDISC data sets.

PK concentrations and PK parameters excluded from summary statistics will not be included in mean/median figures. Mean plots will only contain values where $n > 2$.

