16.1.6 Presentation of PK Concentration and PK Parameter Data

16.1.6.1 Listings and Tables

The following PK tables will be produced (PK Analysis Set):

- Descriptive statistics of plasma concentrations by nominal time and study intervention
- Descriptive statistics of plasma PK parameters by study intervention

The following PK Listings will be produced (Safety Analysis Set):

- Individual plasma concentrations by nominal time, participant, and study intervention sorted in chronological order
- Individual plasma PK parameters by participant and study intervention
- PK sampling date, actual time, nominal time, deviation from time, percentage time deviation by participant, and study intervention sorted in chronological order
- Phoenix® WinNonlin® NCA Core Output

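### Does setting BLQ concentrations to zero make the geometric statistics in SAP 16.1.1 unworkable?

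*SAP*

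**What the plan says.** SAP 16.1.1 lists the summary statistics for evobrutinib concentrations. Besides the arithmetic ones it asks for "geometric mean (GeoMean), the geometric coefficient of variation (GeoCV%) and the 95% confidence interval (CI) for the GeoMean". Its next sentence counts BLQ values in n and sets them to zero: "a measurement of BLQ represents a valid measurement and will be taken as zero for summary statistics of PK concentration data". SAP 16.1.4 repeats the rule more widely: "Values BLQ will be taken as zero for summary statistics of PK concentration data, PK parameter estimation (e.g., AUC) and for graphical presentations". Neither section makes an exception for statistics computed on the log scale.

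There is one display rule, also in 16.1.1: "Any mean or median value that is below the lower limit of quantification will be shown as BLQ". It names means and medians. It does not mention the geometric CV or the confidence limits.

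The table concerned is the one SAP 16.1.6.1 describes as "Descriptive statistics of plasma concentrations by nominal time and study intervention".

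**The concern.** Two instructions in one paragraph cannot both be carried out when a row contains a BLQ value. A single zero makes the product of the values zero, and its logarithm does not exist. Three of the requested statistics are then degenerate or undefined, and the SAP does not say what to put in the cells.

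If programmers filled the gap differently, the same data could give different tables. Leaving zeros out of the log statistics would also make the geometric mean rest on fewer values than the n printed beside it. At stake are the reproducibility and internal consistency of one descriptive table.

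**Working it through.** The plan states no figure on this point, so there is none to reproduce. The check counts the affected rows, shows what happens in them, and traces where the statistics are used.

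**1. Size of the table.** Protocol 1.3 (Schedule of Activities) samples "at predose and 0.25, 0.5, 1.0, 1.5, 2.0, 2.5, 3.0, 4.0, 6.0, 8.0, 12.0, 16.0, and 24.0 hours postdose". That is 1 + 13 = 14 nominal times. With 4 batches the table has 14 × 4 = 56 rows. Protocol 6.3.1 allocates participants "with a maximum of 7 participants assigned to each treatment sequence", so a row holds at most 4 × 7 = 28 values.

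**2. Rows in which zeros must be expected.** The four sequences in Protocol 6.3.1 (ABCD, BDAC, CADB, DCBA) begin with A, B, C and D once each. In each batch's predose row, up to 7 of 28 values (25%) are therefore taken before any study dose. Protocol 5.2, criterion 16, excludes people who "have participated in a study evaluating a BTK inhibitor within 60 days", so these values should be BLQ. The other 21 follow a washout of about 48 hours. All 4 predose rows should therefore contain zeros, whatever remains from the previous dose: 4/56 = 7.1% of rows.

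**3. Postdose rows.** The other 52 rows may contain BLQ values at the earliest or latest times, but the documents give no limit of quantification, half-life or BLQ rate. With an assumed rate p, equal and independent across values, P(at least one BLQ in 28) = 1 − (1 − p)^28. This is 25% for p = 1% and 95% for p = 10%. These figures do not describe this trial: BLQ values would cluster at the ends of the profile and be rare near the peak, so no single p fits 52 rows.

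**4. What one zero does.** With m and s the mean and SD of ln x:

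- GeoMean = exp(m), equivalently the n-th root of the product
- GeoCV% = 100 × √(exp(s²) − 1)
- 95% CI = exp(m ± t × s/√n)

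The row below is simulated for illustration only (n = 28, lognormal, true median 100, log SD 0.5). For the last line an LLOQ of 1 is assumed.

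| Handling of one BLQ value | GeoMean | GeoCV% | 95% CI |
|---|---|---|---|
| No BLQ value in the row | 95.8 | 45.6 | 80.9 to 113.4 |
| Set to zero, as the SAP says | 0 (product form) | undefined | undefined |
| Left out, n = 27 | 95.0 | 46.3 | 79.8 to 113.1 |
| Replaced by LLOQ/2 | 78.8 | 149.1 | 51.8 to 119.8 |

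With the zero in place the arithmetic mean moves from 103.6 to 99.4 and the median from 100.9 to 96.3. Both remain well defined.

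**5. Which of these the SAP allows.** The last two lines each break the written rule: one drops a value that 16.1.1 counts as valid, the other replaces the prescribed zero. Only the second line follows the SAP. There the geometric CV and the interval can only be shown as not calculable. The geometric mean, if it counts as a mean under the display rule, appears as BLQ. What is left open is a cell label.

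**6. Where the statistics are used.** SAP 16.1.3 models log Cmax and log AUC0-∞, which are participant-level parameters. The mean and median curves in SAP 16.1.6.2 are arithmetic means and medians. The geometric summaries in SAP 16.1.2 are of PK parameters, not of concentrations by time. No planned comparison or figure takes a geometric concentration statistic as input.

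**The case for a change.** The strongest case for a change is that an analysis plan exists to settle technical detail, and this detail is unsettled. Software that treats the logarithm of zero as missing would drop the zeros without warning, so the geometric mean would rest on fewer values than the printed n. The table in the working shows that the handling matters: 95.0, 78.8 or 0 for the same row. The display rule does not reach the geometric CV or the limits. Where one value in 28 is BLQ, it would also show the geometric mean as BLQ although 27 values are quantifiable. The rounding list in 16.1.1 has no format for the three statistics, while the list in 16.1.2 does, which suggests they were carried over from the parameter section. One sentence would close the gap.

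The textual point stands: no section exempts log-scale statistics, and two of the three have no display rule. Silent dropping is a real programming trap, but it would depart from a rule the SAP states, and it is a matter for checking the table program.

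The obvious remedies gain nothing. Marking the cells as not calculated gives what the zero rule already forces. Removing the three statistics from the concentration table would also lose them in rows without BLQ values, where they work. In a postdose row with an occasional BLQ value, the arithmetic mean, SD, CV, median, minimum and maximum remain.

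**Conclusion.** The inconsistency is genuine but editorial, and no change to the plan follows. It is shown for 4 of 56 rows, all predose, where a geometric mean or CV carries no information on relative bioavailability. For the other 52 rows the extent is unknown. Wherever a BLQ value occurs, up to three cells are shown as BLQ or not calculable and the rest of the row is intact. The primary batch comparisons, their 90% confidence intervals and the study's conclusions are unaffected.

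This rests on two assumptions. The first is that samples taken before any study dose are BLQ, as criterion 16 leads one to expect. The second is that the programmer keeps to the zero rule and marks uncomputable cells as such, the ordinary practice for a table of this kind.
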